4.2 IN PATIENT SAFETY ENDPOINTS

- BARC definition for bleeding (see appendix 1)
- Target Vessel Failure
- Vital Status at Discharge

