8. END OF STUDY

End of the study will be marked by the last patient's last visit samples when they have been analysed. The data will then be scrutinised, and finally an article summarising the study written and submitted to a peer-reviewed journal for consideration of publication. Positive trial results might lead to implementation of the use of intravenous Cangrelor in clinical practice.

Study termination

The safety monitoring committee/Steering Committee will meet on a regular basis. The trial will be terminated early if there is evidence of unexpected excess bleeding with cangrelor or severe or unexpected complications from the IMR procedure.

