9. ADVERSE EVENTS

9.1 **DEFINITIONS**

9.1.1 Adverse Event (AE): any untoward medical occurrence in a patient or clinical study subject. Adverse events will stop being recorded after 36 hours from the index admission.

9.1.2 Serious Adverse Event (SAE): any untoward and unexpected medical occurrence or effect that:

- Results in death
- Is life-threatening refers to an event in which the subject was at risk of death at the time of the event; it does not refer to an event which hypothetically might have caused death if it were more severe
- Requires hospitalisation, or prolongation of existing inpatients' hospitalisation
- Results in persistent or significant disability or incapacity
- Is a congenital anomaly or birth defect

Common expected post-procedural adverse events listed below are the conditions not going to be classed as SAEs:

- Acute renal failure requiring haemodialysis, peritoneal dialysis or haemofiltration
- Ventricular arrhythmia requiring direct-current (DC) cardioversion
- Atrial arrhythmia requiring intervention
- Significant heart block requiring temporary or permanent pacing
- Cardiac tamponade requiring urgent surgical intervention
- Cardiogenic shock requiring intra-aortic balloon pump or other assist device
- Emergency coronary artery bypass graft operation

- Arterial complications
- Blood or platelet transfusion

Medical judgement should be exercised in deciding whether an AE is serious in other situations. Important AEs that are not immediately life-threatening or do not result in death or hospitalisation but may jeopardise the subject or may require intervention to prevent one of the other outcomes listed in the definition above, should also be considered serious.

9.2 **REPORTING PROCEDURES**

All serious adverse events will be reported. Depending on the nature of the event the reporting procedures below will be followed. Any questions concerning serious adverse events reporting will be directed to the Chief Investigator in the first instance.w3433;

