

15 APPENDICES:

15.1 Appendix 1 – The Bleeding Academic Research Consortium (BARC) proposes 5 bleeding types (67)

- Type 0: no bleeding
- Type 1: bleeding that is not actionable and does not cause the patient to seek unscheduled performance of studies, hospitalization, or treatment by a healthcare professional; may include episodes leading to self-discontinuation of medical therapy by the patient without consulting a healthcare professional
- Type 2: any overt, actionable sign of haemorrhage (eg, more bleeding than would be expected for a clinical circumstance, including bleeding found by imaging alone) that does not fit the criteria for type 3, 4, or 5 but does meet at least one of the following criteria: (1) requiring nonsurgical, medical intervention by a healthcare professional, (2) leading to hospitalization or increased level of care, or (3) prompting evaluation
- Type 3
 - Type 3a
 - Overt bleeding plus haemoglobin drop of 3 to <5 g/dL* (provided haemoglobin drop is related to bleed)
 - Any transfusion with overt bleeding
 - Type 3b
 - Overt bleeding plus haemoglobin drop $\geq 5 \text{ g/dL}^*$ (provided haemoglobin drop is related to bleed)
 - Cardiac tamponade

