Appendix 2: Study Summary Tables

	1	2	3	4	5	6	7	8
Timepoint reference	Prior to PPCI	First IC balloon inflation	End of PPCI (following the life-saving part)	90-120 minutes post PPCI	4 hours post dosing	24-36 hours post dosing (15 ml blood for VASP/VerifyNow and peak Troponin)	Discharge	Three months post PPCI
Eligibility	X							
Medical History	x							
Verbal Assent	x							
Randomisation	x							
Dispensation of treatment	Х							
Initiation of either oral Ticagrelor or IV Cangrelor therapy	X							
Written Informed consent			Х					
Demographic data collection	X							
10ml blood collection for VASP/ VerifyNow		×			X	X		
IMR			Х					
ECG				X				

10ml blood								
collection for						x		
Peak Troponin						^		
Level (routine)								
TIMI Flow			X					
Grade								
Vital Status assessment							X	Х
BARC definition for bleeding			x					
Target Vessel Failure			X					
CMR								Х
Concomitant Medications	X	X	X	X	x	X	X	Х
Adverse Events review	Х	X	X	X	X	X to stop at 36 hours		

Study Steps	Time
1-Quick initial assessment of patients suitable for enrollment in the trial	Upon arrival at the Heart and Lung centre, New Cross Hospital
2-Verbal assent	After the initial assessment
3-Randomisation to either one of the two trial treatment groups	After obtaining verbal assent
4-Initiation of either oral Ticagrelor or IV Cangrelor therapy	Based on randomisation result
5-Primary PCI procedure	Once the second antiplatelet therapy is initiated (Ticagrelor or Cangrelor)
6-Blood sampling for P2Y12 inhibition estimation (using VASP phosphorylation and VerifyNow tests)	A- At the time of first intracoronary balloon inflation (10 ml of blood from the femoral or radial sheath) B- 4 hours post dosing (10 ml of blood from an anticubital vein) C- 24-36 hours post dosing (15 ml in total. 10 ml for VASP/VerifyNow and 5 ml for peak Troponin level. One needle prick)
7-IMR measurement	Immediately following PPCI (same procedure setting)
8-Patient information sheet will be provided and written consent sought	After successful completion of PPCI
9-ECG recording to assess the degree of ST-segment resolution.	90-120 minutes post PPCI

10-Peak Troponin level assessment	24-36 hours post PPCI.
11-TIMI flow grade assessment	Post PPCI
12-Vital Status assessment	On discharge and at three months post PPCI
13-CMR estimation of final myocardial infarct size	At three months post PPCI

STUDY COSTS

CMR	100 scans @ reduced research rate £100	= £10,000

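### BARC bleeding is an in-patient endpoint, but it is scheduled for grading only at the end of PPCI, and adverse event recording stops at 36 h

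*Combined protocol and SAP*

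**What the plan says.** Section 4.2 places BARC bleeding, defined in Appendix 1, under in-patient safety endpoints. Its heading implies a window that runs to discharge.

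The schedule in Appendix 2 has a row "BARC definition for bleeding" with a single mark, in the End of PPCI column. The list of study steps in the same appendix adds no other BARC assessment. The discharge column carries only vital status and concomitant medications.

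On collection, section 9.1.1 says: "Adverse events will stop being recorded after 36 hours from the index admission". The adverse event row of Appendix 2 agrees ("to stop at 36 hours"). Within that window, section 9.2.1 has all non-serious events recorded.

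Section 9.2 has all SAEs reported and gives no cut-off time for them. Section 9.1.2 then makes exceptions: "Common expected post-procedural adverse events listed below are the conditions not going to be classed as SAEs". That list includes "Blood or platelet transfusion", arterial complications, and tamponade that needs urgent surgery. In Appendix 1, "Any transfusion with overt bleeding" is BARC type 3a and tamponade is type 3b.

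Section 8 makes bleeding a reason to stop: "The trial will be terminated early if there is evidence of unexpected excess bleeding with cangrelor".

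**The concern.** An endpoint defined over the hospital stay needs assessments that cover the stay. Here the only scheduled grade comes at the end of the procedure. Under section 6.2.2, cangrelor runs for at least two hours, and that arm's ticagrelor load is given half an hour before the infusion ends. The one grade can therefore fall before the antiplatelet exposure being studied is complete.

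What is at stake is the safety description by arm. BARC is the only bleeding scale in the plan, and excess bleeding with cangrelor is an early termination criterion. Followed literally, the schedule gives the committee and the final report graded bleeds around the procedure, adverse events with no scheduled grade up to 36 h, and only partial collection after that.

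**Working it through.** The plan has no figure to reproduce, so the check sets the rules side by side and adds simple timing arithmetic.

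**1. Is the single mark really at the end of PPCI?** The table was read by program, so its columns were checked against rows whose timing is stated in the study steps. IMR falls in the End of PPCI column (step 7), ECG in the 90-120 minute column (step 9), and vital status in the discharge and three-month columns (step 12). The alignment holds. BARC is marked at 1 of the 6 time points from first balloon inflation to discharge. The column is not strictly an instant, because written consent is marked there too and section 5.1 has it sought after the patient has rested. It still precedes the 90-120 minute column.

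**2. Inputs.**
- From the documents: infusion at least 120 min and at most 180 min; ticagrelor load 30 min before it stops (6.2.2); platelet function normal within 60 min of stopping cangrelor (2.1); adverse event stop at 36 h = 2160 min (9.1.1).
- Assumed, because the documents give no values: end of PPCI at T = 30 to 90 min after infusion start; d = 10 to 30 min from admission to infusion start; discharge at 36 to 96 h.

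**3. What is still to come at the mark (2-hour infusion).**
- Infusion left = 120 − T = 90, 60, 30 min for T = 30, 60, 90.
- Ticagrelor load at 120 − 30 = 90 min, so 60, 30 or 0 min after the mark.
- Time until cangrelor's effect has gone = 120 + 60 − T = 150, 120, 90 min.
- On the widest reading of the column (up to 120 min after PPCI), the grade falls T + 120 = 150 to 210 min after infusion start. By then a 2-hour infusion has ended and the load has been given.
- If the procedure outlasts two hours, the infusion is extended to match it, up to three hours. The statement is therefore that the infusion *may* still be running.

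**4. Share of the 36 h window after the only mark.**
- Strict reading, 2160 − (d + T): from 2160 − 40 = 2120 min (35.3 h, 98.1%) to 2160 − 120 = 2040 min (34.0 h, 94.4%).
- Widest reading, 2160 − (d + T + 120): from 2160 − 160 = 2000 min (33.3 h, 92.6%) to 2160 − 240 = 1920 min (32.0 h, 88.9%).

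These are shares of clock time. They do not give the share of bleeds, which may cluster around the procedure.

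**5. When do the arms stop differing?** At the latest, d + 180 + 60 = 30 + 240 = 270 min = 4.5 h after admission. From then both arms are on ticagrelor alone, which leaves 36 − 4.5 = 31.5 h before recording stops.

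**6. Hospital stay after 36 h.** Discharge at 36 h: 0 h. At 48 h: 12 h (25% of the stay). At 72 h: 36 h (50%). At 96 h: 60 h (62.5%).

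**7. Routes by which a bleed reaches the data.**

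| Bleed | End of PPCI to 36 h | 36 h to discharge |
|---|---|---|
| Non-serious | Adverse event; no scheduled grade | No stated route |
| Handled as transfusion, arterial complication or tamponade needing urgent surgery | Adverse event; no scheduled grade | Listed as not an SAE; may not be collected |
| Other serious | Adverse event or SAE; no scheduled grade | May be reported as an SAE; no scheduled grade |
| Fatal | Also shown by vital status | Also shown by vital status |

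**The case against.** The case for leaving the plan alone has real weight.

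- **Bleeds up to 36 h are not lost.** A reader might infer that they are. BARC is a classification applied to recorded events; these bleeds are recorded and could be graded later. Section 4.2 already commits to BARC for the in-patient period. Target vessel failure has the same lone mark, which suggests table shorthand or a slip. This stands. What remains is that no later grading is scheduled.
- **Serious bleeds after 36 h need not go unreported.** The 36 h sentence sits in the adverse event definition, and SAE reporting has no stated cut-off. Prolonged hospitalisation is an SAE criterion, and section 9.1.2 lets medical judgement treat important events that need intervention as serious. This stands in part: the exempted events still overlap with BARC types 3a and 3b.
- **The 36 h stop does not hide a cangrelor effect.** Another tempting inference is that excess bleeding with cangrelor would fall in the uncollected period. Step 5 argues against it: later bleeds occur on the same drug in both arms, apart from some that present late.
- **The termination criterion does not require BARC grades.** The committee can act on adverse events. This stands, but ungraded events are harder to compare between arms.
- **Type 3 grading is not shown to be impossible.** A reader might infer this because no haemoglobin test is scheduled. The documents do not say whether routine counts are available, so the inference is unsupported.

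**Conclusion.** The concern holds in a limited form. The schedule as written does not deliver BARC bleeding over the in-patient period that section 4.2 names.

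The more important part is the first 36 hours. Bleeds after the end of PPCI are recorded there without a scheduled grade, and this window contains all of the time in which the randomised treatments differ. For a 2-hour infusion and a mark read strictly as the end of the procedure, 90 to 150 min of that time follow the mark, with T assumed to be 30 to 90 min. On the widest reading of the column, little or none does.

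The gap after 36 h mainly leaves the endpoint incomplete. It is limited to non-serious bleeds and those handled through the exempted events, and it is empty for patients discharged by 36 h.

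No patient count can be derived, because the documents give no bleeding rates, timing of bleeds, procedure duration or length of stay. Section 4.1 says the study is not powered for clinical outcomes, so the value of these data lies in a complete description by arm. The change is worth making because it is cheap; the defect does not undermine the trial.

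**What to change.** - **Appendix 2:** keep the End of PPCI BARC mark and add BARC at 24-36 h and at discharge, in both arms. Each added grade should cover all bleeds since the previous one.
- **Section 9.1.1 and Appendix 2:** record overt bleeding to discharge, including bleeding treated by transfusion. Keep the 36 h stop for other adverse events.
- **Section 7:** report counts by BARC type and arm, descriptively.

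The cost is two extra form entries per patient (2 × 100 = 200 in all), one descriptive table, and a minor protocol amendment, which needs ethics committee approval under section 10.1. No blood test, needle or visit is added.
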